MIneralocorticoid Receptor Antagonism for CardiovascuLar hEalth in HIV The MIRACLE HIV Study

grant demonstrate a mean change in MCP-1 of 44.0 ± 41.8 pg/mL between a low sodium and ad lib sodium diet. Based on this SD, the proposed study, with a sample size of 42 subjects, and therefore 36 evaluable subjects considering a 15% attrition rate, will attain 85% power at a two sided α of 0.05 to detect a difference of at least 44.0 pg/mL in mean MCP-1 between the formally tested RAAS activated (sodium restricted) and RAAS suppressed (sodium loaded) states. For other biomarkers, we have 85% power at a two-sided 0.05 α level to show a change of at least 0.95 SD between RAAS activated and suppressed states.

Aim V: For this aim, the endpoint is change in TBR assessed by cardiac ^{18}F -FDG-PET/CT. Secondary endpoints include: change in hsCRP, pentraxin3, IL6, Lp-PLA2, MCP-1, sCD14, sCD163. Statistical algorithms as detailed in Aim I will be applied to these specific endpoints. Similar to Aim I, changes in TBR and inflammatory biomarkers over 12 mos comparing eplerenone vs. placebo will be assessed using ITT and longitudinal linear effects modeling with imputation and sensitivity analyses. We will also determine whether longitudinal changes in arterial inflammation are associated with changes in biomarkers of inflammation and immune activation to understand the potential relationship of these inflammatory indices as markers of improved indices of the coronary vasculature in response to MR blockade in the HIV. **Sample Size**

Determination: In our prior studies assessing arterial inflammation on ^{18}F -FDG PET, the mean \pm SD (95% CI) TBR at baseline among HIV subjects was 2.23 ± 0.45 (2.07, 2.40)mm 3 .⁷⁴ In order to estimate the SD of change in TBR, we assumed the intrasubject longitudinal correlation over time $r=0.75$, which results in a conservative SD estimate of 0.34. This study enrolling 42 subjects with 36 evaluable subjects will attain 85% power at a two sided α of 0.05 to detect a difference in mean TBR changes of 0.32 between eplerenone vs. placebo, a clinically relevant difference in the changes as our preliminary data show that non-HIV subjects have a mean TBR 1.89. For biomarkers, this study has 85% power at a two-sided 0.05 α level to show a mean change of at least 0.95 SD after treatment with eplerenone vs. placebo.

Aim VI: In an exploratory analysis, subjects will be enrolled using a factorial sampling strategy into 4 analytic strata (low VAT/absence of plaque, low VAT/presence of plaque, high VAT/absence of plaque, high VAT/presence of plaque). Using this design, we will first analyze whether there are differences in markers of inflammation and heart disease by VAT status (main effects model comparing presence and absence of excess VAT) using student's t-test for variables that are normally distributed or Wilcoxon rank sum test for variables that are not normally distributed. Based on the exclusion criteria excess VAT is determined to be $>110\text{cm}^2$. After assessing for differences in VAT in the main effects model, we will examine the degree to which markers of inflammation and heart disease are related to coronary plaque in both the high and low VAT groups, and whether this relationship is stronger in the coronary plaque group as a result of increased VAT using ANOVA for variable that are normally distributed and Kruskal-Wallis Test for variables that are not normally distributed.

VII. Risks and Discomforts

Blood Drawing: The total blood drawn for subjects completing the study is equivalent to approximately 560 ml (over a period of 12 months). This quantity of blood drawing does not pose excessive risk to subjects. By comparison, the Red Cross allows a healthy adult to donate 1 pint of blood every 8 weeks, which is about 473 ml. Subjects with a hemoglobin < 10 mg/dL will be excluded from the study. There will be minimal risk and

Mineralocorticoid Receptor Antagonism for Cardiovascular Health in HIV The MIRACLE HIV Study

discomfort associated with blood drawing and IV placement. The risks of these procedures are minor bruising or bleeding at the site of the blood draw or IV catheter or feeling faint. Standard clean insertion techniques will be utilized to minimize risk of infection.

Intravenous Catheter Placement: There are minor risks and discomforts associated with having an intravenous line and with injection of contrast agent through the intravenous line, including the possibility of bleeding, pain, inflammation (redness and swelling), and leaking of contrast agent outside of the vein at the site of the IV. These problems usually self-resolve or only require minor treatments, such as application of an ice-pack or slight pressure for a few minutes.

CT Abdomen: This study is obtained once during the screening process to evaluate for visceral adipose tissue area. The radiation risk associated with the single slice CT scan of the abdomen is approximately 0.55 mSv. This is equivalent to the amount of radiation an individual would normally get in 2 months from natural background sources from the earth and the sky. As with the other imaging studies, there may be incidental findings on the CT study. If any of these findings are clinically significant, the subjects will be withdrawn from the study and referred to the primary care physician for further evaluation.

Coronary CTA and Radiation: With the implementation of measures to limit radiation exposure, the total dose of the coronary CTA examination will be approximately 4 mSv, depending on the weight, gender and heart rate. The added radiation from the two CTA scans (screening and follow-up) will be 8 mSv. This is equivalent to the amount of radiation an individual would normally get in 2 years and 7 months from natural background sources from the earth and the sky. State-of-the-art dose reduction techniques at MGH allow the dose to be substantially lower than historically reported median coronary CTA doses. Iterative image reconstruction algorithms allow for further reductions in radiation dose. These techniques allow for up to a 50% reduction in radiation dose compared with previous generation protocols. Massachusetts General Hospital was the first hospital in New England to use the Siemens Definition Flash second-generation dual-source 128 or Siemens SOMATOM Force dual-source 196 detector-row CT, an advanced cardiac-capable CT scanner which allows ultra-fast cardiac imaging at the lowest possible radiation doses potentially equivalent to or less than a chest CT scan. HIV patients may have clinically significant subclinical CAD. We will assess the first coronary CTA for this condition. Any subject with evidence of severe coronary artery stenosis, defined as $\geq 50\%$ stenosis in the left main coronary artery or $> 70\%$ stenosis in the other major coronary arteries will be withdrawn from the study prior to further evaluative imaging and procedures and prior to randomization to study drug. Subjects with evidence of clinically significant atherosclerosis will be referred to a cardiologist for appropriate evaluation and treatment.

CTA contrast medium: CTA requires the intravenous administration of iodinated contrast medium. These contrast media have been known to cause renal failure, particularly in subjects with a pre-existing renal impairment. Adequate hydration will also be emphasized to each study participant. The contrast dose in coronary CTA has decreased with the introduction of faster scanners. The dose required will be between 60 to 100 ml. Allergic reactions to iodinated contrast media may cause skin reactions or in very rare occasions result in breathing difficulty and hypotension. Subjects will be closely

Mineralocorticoid Receptor Antagonism for Cardiovascular Health in HIV The MIRACLE HIV Study

monitored for the development of any allergic reactions. To minimize risk from iodinated contrast, subjects with previous allergic reactions to iodine-containing contrast media or signs of renal failure or history of renal disease will be excluded from the CTA study. Additional safety criteria will be implemented by measuring serum creatinine and excluding subjects with serum creatinine >1.5 mg/ml or estimated GFR <60 mL/min/1.73m 2 . Metformin use is an exclusion criteria for the study, so the risk of lactic acidosis will be avoided.

Nitroglycerin: Nitroglycerin is commonly used in subjects with angina pectoris and is generally considered safe. The side effects and risks of nitroglycerin are generally mild and of short duration and include hypotension, tachyarrhythmia, headache, lightheadedness, and visual disturbance. Subjects who are on sildenafil, tadalafil, or vardenafil (PDE5 inhibitor) will need to stop these drugs at least 5 days prior to receiving nitroglycerin on the day of the coronary CTA scan. If baseline systolic blood pressure is below 90, nitroglycerin will not be given. If a participant's blood pressure were to drop precipitously or if the participant develops symptoms, standard clinical care will be provided. Other contraindications to nitroglycerin include severe aortic stenosis or hypertrophic obstructive cardiomyopathy.

Cardiac PET and Radiation: The two cardiac PET scans will involve exposure to radiation for research purposes. Subjects will receive a research related rest and stress ^{13}N -ammonia PET scan before and after a mineralocorticoid receptor antagonist. ^{13}N -ammonia (20 mCi) will be injected twice prior to rest and stress scans. Each PET scan will expose subjects to 3.36 mSv of radiation. The added radiation from the two PET scans (baseline and follow-up) will be 6.72 mSv. This is equivalent to the amount of radiation an individual would normally get in 2 years and 2 months from natural background sources from the earth and the sky. The radioactive tracer will be administered at baseline and at 12 months. HIV patients may have silent ischemia. We will assess the first regadenoson/adenosine-stimulated coronary blood flow study for this condition. Any subject with evidence of clinical significant ischemia will be withdrawn from the study prior to further evaluative studies and prior to randomization to study drugs. Subjects with evidence of ischemia will be referred to a cardiologist for appropriate evaluation and treatment. In addition, there may be incidental findings on the PET study. If any of these findings are clinically significant, the subjects will be withdrawn from the study and referred to the primary care physician for further evaluation.

Regadenoson/Adenosine: Regadenoson or adenosine will be administered during the cardiac PET and MRI studies. Regadenoson stress and adenosine stress have been used routinely for many years for evaluating patients with known or suspected CAD. Regadenoson and/or adenosine will be administered at the radiologist's discretion. The most common side effects associated with the Regadenoson or adenosine infusion include: flushing, chest pain/pressure, shortness of breath, palpitations, headache, mild hypotension and heart block. These side effects are usually mild and self-limiting. If they are severe in intensity, aminophylline IV (1 mg/kg) will be given as per standard protocol. Subjects will have their blood pressure and heart rate monitored closely by a physician and/or nurse in attendance at all times. The protocol will be immediately discontinued if clinically significant atrial or ventricular arrhythmias are observed.

MIneralocorticoid Receptor Antagonism for CardiovascuLar hEalth in HIV The MIRACLE HIV Study

Radiation Exposure: The total estimated radiation exposure from Aims 1 and 3 is approximately 15.27 mSv. Aim 2 has no specific radiation associated. This is equivalent to the amount of radiation an individual would normally get in 4 years and 11 months from natural background sources from the earth and the sky. To minimize radiation exposure, coronary CTA dose reduction techniques including ECG-triggered tube modulation and automatic exposure control will be applied when possible. Larger patients can get higher doses (up to twice that of an average size patient) from any CT exam compared to the mean dose. If a patient has received previous radiation exposure prior to participation in the study, we will also calculate the total radiation exposure and if prior cumulative exposure during the 12 months prior to the study exceeds 15 mSv (which is 30% of the maximum recommended annual dose for research subjects set by the MGH Radiation Safety Committee), then the subject will be excluded from participating. Pregnancy test will be performed prior to CT or PET scanning in women. (See also sections for coronary CTA and cardiac PET above for specific radiation exposure.)

Abdominal MRI and Cardiac MRI: Subjects will be carefully screened for metal implants such as surgical clips or pacemakers prior to MRI scanning. Sources of discomfort during the MRI study may include noise and possible claustrophobia. Subjects will be given earplugs due to the loud noises during the test. Subjects who feel uncomfortable in confined spaces may have difficulty in the narrow cylinder of the MRI, and the MRI can be stopped at any time at the subject's request. There are no known hazards for pregnant women; however, pregnancy is an exclusion for this study. The MRI has the potential, during normal routine use, to cause localized warming of the skin and the underlying tissues. If the subject experiences discomfort due to warming, the procedure will be stopped. Radio-frequency power deposition is strictly controlled by the scanner software, in conformance with the applicable FDA guidelines, and cannot be overridden by the user. An IV line, placed just prior to the MRI exam, may cause tenderness, swelling, warmth at the injection site, and rarely infection. There is no radiation exposure other than exposure to the magnetic and non-ionizing radio-frequency fields, which meet FDA guidelines. All pulse sequences used for this study have been approved by the hardware vendor for cardiac MRI studies, and received FDA clearance, except for the sequence that is used for perfusion imaging, which is a "works-in-progress" package that has undergone safety testing by Siemens Medical Systems, and been licensed for use to Brigham and Women's Hospital. A single axial slice of the abdomen will be obtained with MRI. The total amount of time in the magnet will be approximately 45 min. For the cardiac MRI, the total amount of time in the magnet will be approximately 80 min. In addition, there may be incidental findings on the MRI study. If any of these findings are clinically significant, the subjects will be withdrawn from the study and referred to the primary care physician for further evaluation.

Gadolinium Contrast: Gadolinium contrast has been widely used and is very well tolerated. Gadolinium will be administered with the cardiac MRI studies. No contrast is administered with the abdomen MRI. The most common adverse reactions of gadolinium are transient headache (3.6%), injection site coldness (3.6%), and nausea (1.5%). There is a very rare occurrence of nephrogenic systemic fibrosis after gadolinium, but this has only been reported in subjects with impaired renal function. All subjects will have a serum creatinine assessed prior to each MRI and subjects with serum creatinine >1.5 mg/ml or estimated GFR<60 will be excluded from the study. For this study a macrocyclic Gd-contrast agent will be used (Gadoterate meglumine, DOTAREM,

MIneralocorticoid Receptor Antagonism for CardiovascuLar hEalth in HIV The MIRACLE HIV Study

Guerbet) which has the highest thermodynamic stability constant among all available gadolinium-bound contrast agents to reduce the chance of any exposure to Gd³⁺ ions.

Incidental Findings: Incidental non-coronary and coronary findings may be obtained, and significant non-coronary and coronary findings will be communicated to the subject and provider as appropriate.

Standardized High Sodium Diet: Select subjects will be receive broth packets for 3 days. Increases in dietary sodium may cause mild elevations in blood pressure, but usually only by a small amount depending upon the subjects' salt-sensitivity status. Blood pressure will be monitored frequently during study visits. Procedures will not be initiated if the subject's blood pressure is too high or symptoms are present. When subjects resume their usual home diets, blood pressure is expected to return to baseline.

Medications: Administration of all medications will be conducted by the appropriate health care professional. A physician will be available on-call 24 hours/day, 7 days/week, to all study participants for any questions or concerns.

Eplerenone: The eplerenone dose of 50mg daily has been used safely in previous studies to improve coronary circulation in individuals with Type 2 diabetes and by others in numerous studies of patients with CVD. This dose is FDA approved for indefinite use in patients with hypertension or left-ventricular dysfunction following myocardial infarction. Hyperkalemia is a potential side effect of eplerenone use, and any subject with serum K > 5.5 mEq/L at screen will be excluded. During the study, a subject who has an elevated K of > 5.5 mEq/L at any study visit will have a recheck; if the K remains elevated after recheck, the dose will be decreased to 50mg daily. If the K remains elevated > 5.5 mEq/L, the subject will be excluded from the study. Additionally, subjects who experience symptoms of hyperkalemia and have a K > 5.0 mEq/L will be excluded from continued participation in the study. Subjects who have hypotension (SBP<90 mmHg) at any study visit after titration to full dose eplerenone 50mg twice daily will be given a dose reduction to 50 mg daily. If a subject remains hypotensive (SBP <90 mmHg) or symptomatic of hypotension at the reduced dose they will be dropped from the study. Since subjects with renal insufficiency may require reduced dosing based on creatinine clearance, subjects with serum creatinine > 1.5 mg/dl will also be excluded. Other rare side effects include dizziness, fatigue, and diarrhea; these will be assessed for throughout the study. The effect of eplerenone on an embryo, fetus, or on a breastfeeding infant, is unknown and may be harmful. Because of these unknown risks, women cannot take part in this study if they are: pregnant, trying to become pregnant, breastfeeding. If women become pregnant or think they are pregnant during the study, they must stop taking the study medication and will be withdrawn from the study. We have received FDA IND exemption for the use of eplerenone in HIV for insulin resistance and recently received an FDA IND exemption for application in CVD indices in HIV. Protease inhibitors with the most significant effect on CYP3A4 will be exclusionary as in our prior trials of HIV patients. We will also exclude subjects using other strong inhibitors of CYP3A4, as well as CYP3A4 inducers. Furthermore, all subjects will be carefully monitored for side effects, including frequent potassium and BP monitoring. A 50mg twice daily dose of eplerenone has been chosen, such that even if concentrations do increase somewhat through pharmacokinetic interactions, we expect the drug to be well tolerated. The dose of 100 mg/day has been effective in numerous studies of non-HIV patients and is expected to be effective in the proposed studies.

**Mineralocorticoid Receptor Antagonism for Cardiovascular Health in HIV
The MIRACLE HIV Study**

Optional Substudy--Cardiac 2-deoxy-2-18F-Fluorodeoxyglucose Positron Emission Tomography/Computed Tomography (18F-FDG-PET/CT) and Radiation:

The two cardiac PET/CT scans will involve exposure to radiation for research purposes. Subjects will receive a scan before and after a mineralocorticoid receptor antagonist. For ¹⁸F-FDG-PET/CT, the administered dose from ¹⁸F-FDG for a typical cardiac study is 370 MBq (10 mCi=7.03 mSv) and the effective dose for an attenuation correction scan of head/neck/upper abdomen is about 1.58 mSv. The total effective dose from two FDG-PET/CT studies would be 17.22 mSv. This is equivalent to the amount of radiation an individual would normally get in 5 years and 7 months from natural background sources from the earth and the sky. A STAT serum pregnancy test will be performed on the day of prior to commencement of the study. In addition, there may be incidental findings on the PET study. If any of these findings are clinically significant, subjects will be informed, referred to their primary care physician for further evaluation, and withdrawn as appropriate from the study.

Optional Substudy--Radiation Exposure The total estimated radiation exposure for the entire study (main study+substudy) would be 32.49 mSv. This is equivalent to the amount of radiation an individual would normally get in 10 years and 6 months from natural background sources from the earth and the sky. (See also sections radiation exposure for other precautions and cardiac ¹⁸F-FDG-PET/CT above for specific radiation exposure related to the substudy.)

Optional Substudy--Blood draw The total amount of blood drawn for the substudy will be approximately 4 mL over 1 year for females only. This will be a minimal amount added to the main study. The total blood drawn for subjects completing the entire study (main study+substudy) is equivalent to approximately 564ml (over a period of 12 months).

Optional Blood Sampling Visit (for those that do not qualify after completion of both screening visits)--Blood draw The total amount of blood drawn for the Optional Blood Sampling Visit will be approximately 48 ml. This will be a minimal amount added to the screening visits. The total blood drawn for subjects completing this optional visit (screening visits+optional visit) is equivalent to approximately 73 ml.

VIII. Potential Benefits

There are no direct benefits related to participation in the study, but subjects will receive regular physical exams with blood pressure monitoring, lifestyle counseling to improve nutrition and physical activity, and screen testing that will evaluate for clinically significant coronary artery disease. There may be potential improvements in CVD and inflammation as a result of treatment with eplerenone and/or lifestyle modification. In addition, all subjects will be provided with tools to help them meet the prescribed goals, including a core curriculum binder. Clinically interpretable information on metabolic parameters will be provided to the subject and may help subjects and their clinicians to better understand their metabolic risk if they choose to obtain such information. Any abnormal testing will be conveyed to the subjects' primary care physicians with their permission. In addition, information obtained from this study will benefit HIV patients in the future. Therefore, the benefits of this study are felt to outweigh its risks described above.

Mineralocorticoid Receptor Antagonism for Cardiovascular Health in HIV The MIRACLE HIV Study

For those who do not qualify and choose to participate in the optional blood sampling visit, there are no direct benefits, but subjects will receive screen tests that will evaluate clinically for visceral fat and coronary artery plaque and inform their medical history. In addition, information obtained from the stored blood will benefit HIV patients in the future. Therefore, the benefits of this study are felt to outweigh its risks described above.

IX. Monitoring and Quality Assurance

Written informed consent for this protocol will be obtained from all subjects at the first screening visit, prior to any procedures or interventions. In all cases, consent will be witnessed by an appropriate health care professional (investigator/co-investigator staff). All efforts will be made to insure the privacy rights of the subject. No written or oral communication will be made about any subject with anyone other than the subject, unless the subject so requests. Medical information obtained from the study may become part of the subject's permanent hospital record, subject to the confidentiality and privacy regulations of the Massachusetts General Hospital. Subjects will be closely monitored to ensure that study participation is not adversely affecting their quality of life, and any adverse events will be reported in a timely fashion and in accordance with the Partners HRC guidelines for adverse event reporting. PHRC requires the reporting of unanticipated problems, including risks, within 5 working days or 7 calendar days. Kidney function and potassium levels will be serially monitored. If a subject experiences an opportunistic infection or any acute illness, the lifestyle modification program will be held while the subject is acutely ill.

Hyperkalemia is a potential side effect of eplerenone use, and contraindications for the use of eplerenone include serum K > 5.5 mEq/L at initiation. Therefore, any subject with serum K > 5.5 mEq/L at screen will be excluded from the study. During the study, a subject who has an elevated K of > 5.5 mEq/L at any study visit will have a recheck; if the K remains elevated after recheck they will be excluded from the study. Additionally, subjects who experience symptoms of hyperkalemia and have a K > 5.0 mEq/L will be excluded from continued participation. Subjects who have symptomatic hypotension at any study visit after titration to full dose eplerenone 50mg twice daily will be given a dose reduction to 50 mg daily. Since patients with renal insufficiency may require reduced dosing based on creatinine clearance, subjects with renal insufficiency (serum creatinine > 1.5 mg/dl) will also be excluded from participation. Other side effects have been reported and include dizziness, fatigue, diarrhea, headache, stomach pain, cough, breast enlargement or breast enlargement, rash, abnormal vaginal bleeding. Rare but serious side effects include chest pain, tingling in arms and legs, loss of muscle tone, weakness or heaviness in legs, confusion, lack of energy, cold, gray skin or irregular heartbeat. These potential side effects will be assessed for throughout the study. Exclusion criteria during the study include initiation of ACE-I, ARB, or spironolactone; Hgb < 10; ALT > 3.0x ULN; persistent hyperkalemia (K > 5.5 mEq/L despite recheck and/or symptoms of hyperkalemia if K > 5.0 mEq/L). If a subject remains hypotensive (SBP < 90 mmHg) or symptomatic of hypotension after a dose reduction of eplerenone to 50 mg for this same reason during the study, they will be dropped from the study.

Data Safety Monitoring Plan

Prior to the start of study, a data safety monitoring board will be created and this board will consist of a statistician, a clinician not directly related to the research project, but one who is familiar with HIV infection and its complications, and a member of the HIV community. This board will meet quarterly to review any potential side effects or adverse events in relation to the use of eplerenone or participation in the study. The

Mineralocorticoid Receptor Antagonism for Cardiovascular Health in HIV The MIRACLE HIV Study

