Regional and global coronary blood flow will be assessed using PET imaging. Vasoactive medications and beta-blockers will be withheld on the morning of the study. Subjects will be allowed to continue using nitroglycerin as needed. Studies will be performed after at least 4 hours of fasting. The protocol will take approximately 2.5 hours, including patient preparation. Regional coronary blood flow will be measured at rest and during an intravenous (IV) infusion of regadenoson (0.4mg) or adenosine (0.14 mg/kg/min) using ¹³N-ammonia as a flow tracer. After IV administration of ¹³N-ammonia (20 mCi), serial images will be acquired for 20 min, as previously described. After 30 min, IV regadenoson or adenosine will be infused for 4 minutes. Two minutes into the regadenoson or adenosine infusion, a second dose of ¹³N-ammonia (20mCi) will be injected and images recorded again in the same sequence. HR, BP, and 12-lead ECG will be recorded at baseline and every minute during and after the infusion of regadenoson or adenosine. All images will be analyzed by an expert in cardiac PET blinded to treatment assignment.

Cardiac Magnetic Resonance Imaging (MRI)

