T1 imaging before and after contrast, using a breath-hold, modified Look- Locker imaging (MOLLI) technique, will be used for mapping of the total and segmental extracellular volume fraction to detect expansion of the extracellular matrix. Typical MOLLI acquisition parameters are: TR/TE=2.14/1.07 ms, flip angle=35°, FOV= 340x255mm, matrix=192x144, 107 phase encoding steps, interpolated voxel size= 0.9x0.9x8mm, parallel acceleration factor=2 with 24 reference lines (iPAD), cardiac trigger delay TD=500ms; 206 ms acquisition time per SSFP image read-out. The pre-contrast T1 mapping will use a 5(2)-3 MOLLI scheme, while the post-contrast T1 measurements will use a 4(2)-3(2)-3(2) scheme, where the numbers in brackets indicate the duration of the rest period as a multiple of the R-to-R duration. The post-contrast T1 measurements are interleaved with the other MR protocol components, such that T1 measurements are not performed within less than 5 minutes of a contrast injection to assure contrast-equilibrium between tissue and blood. Multiple T1 measurements are used with regression analysis to obtain an accurate estimate of extracellular volume (ECV) fraction, thereby improving upon the precision of “two-point” measurement protocols.⁶⁶ Only R1 data-pairs with R1 in blood < 3.5 s-1 will be used to meet the conditions of fast transcytolemmal water exchange, underpinning the linear model for ECV.⁶⁷ ECV will be multiplied by LV mass index and reported as ECVi (g/m²). The T1 protocol comprises one pre-contrast measurement, and 3 post contrast measurements as outlined above. Microvascular coronary function via a combination rest/stress MRI perfusion study will be quantified. Study subjects will be administered regadenoson (5 ml containing 0.4 mg regadenoson bolus via IV, followed by flush) or adenosine (400 microgram bolus via IV, followed by flush). A saturation-recovery prepared fast

MIneralocorticoid Receptor Antagonism for CardiovascuLar hEalth in HIV The MIRACLE HIV Study

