Statistical Consideration: Aim I: The primary endpoint is change in CFR assessed by cardiac PET or change in sMBF by cardiac MRI. Secondary endpoints will include the following: change in sICAM and sVCAM. Shapiro-Wilk test will be used to assess for normality of distribution, and variables that are not normally distributed will be appropriately transformed prior to inclusion in multivariable models. We will compare the change in CFR from months 0 to 12 between treatment groups (eplerenone vs. placebo) using student's t-test for variables that are normally distributed or Wilcoxon rank sum test for variables that are not normally distributed. We will also compare changes in sICAM and sVCAM over 12 months between treatment groups using similar statistical methods. In all Aims, for subjects who withdraw after 6 months, but before the final 12 month visit, we will obtain biomarkers and imaging similar to that scheduled for the final 12 month visit if the subject agrees to have end of study testing. The analysis will be intention to treat (ITT). In order to properly handle subjects with missing outcomes (those who withdrew before 12 months), we will apply longitudinal linear mixed effects model analysis with random subject level intercepts and time slopes by which the longitudinal treatment effect can be examined by testing the significance of

Mineralocorticoid Receptor Antagonism for Cardiovascular Health in HIV The MIRACLE HIV Study

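### The PET, MRI and risk sections disagree on how vasodilator stress is given, and the adenosine totals are about 70- to 168-fold apart without explanation

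*Combined protocol and SAP*

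**What the plan says.** Three places in the combined protocol and SAP describe the stress agents.

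- **Section V, Cardiac PET.** Flow is measured at rest and during an intravenous "infusion of regadenoson (0.4mg) or adenosine (0.14 mg/kg/min"). The duration is the same for both agents: "After 30 min, IV regadenoson or adenosine will be infused for 4 minutes". The flow tracer is timed to the infusion: "Two minutes into the regadenoson or adenosine infusion, a second dose of" tracer is injected.
- **Section V, Cardiac MRI.** The agents are "regadenoson (5 ml containing 0.4 mg regadenoson bolus via IV, followed by flush") "or adenosine (400 microgram bolus via IV, followed by flush"). The adenosine amount is not scaled to weight, and no interval from bolus to stress imaging is given.
- **Section VII, Regadenoson/Adenosine.** One paragraph serves both scans: "Regadenoson or adenosine will be administered during the cardiac PET and MRI studies". It describes side effects of an infusion, does not mention a bolus, and leaves the choice of agent to the radiologist.

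On the endpoint, section VI (Aim I) states: "The primary endpoint is change in CFR assessed by cardiac PET or change in sMBF by cardiac MRI". Section I defines CFR as maximally stimulated flow divided by resting flow; sMBF is the stressed flow itself.

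**The concern.** Both scans offer adenosine as the alternative to the same 0.4 mg of regadenoson. The adenosine set against that common amount nevertheless differs by about two orders of magnitude between the two sections, and the delivery differs for both agents. The only reason given for acquiring MRI perfusion alongside PET is spatial resolution, which does not explain a different stress regimen. The bolus wording for MRI also sits badly with a risk paragraph that covers MRI and knows only an infusion.

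Two things are at stake. The first is measurement. Stressed flow is a component of whichever quantity serves as the Aim I primary endpoint, so an unclear stress specification is an unclear specification of that measurement. The second is safety. These are administration instructions for vasoactive drugs, and if one section carries a wrong figure, staff who follow it would give an unintended amount.

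**Working it through.** The plan states no total adenosine amount, so there is no figure of its own to reproduce.

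**Inputs.** PET adenosine rate 0.14 mg/kg/min, infusion time 4 min, tracer at 2 min (section V, Cardiac PET). MRI adenosine 400 microgram = 0.4 mg (section V, Cardiac MRI). Regadenoson 0.4 mg in both. Body weight *w* is not given; 50 to 120 kg is assumed.

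**Formulas.**
- PET total = 0.14 × 4 × *w* = 0.56 *w* mg; ratio to MRI = 0.56 *w* / 0.4 = 1.4 *w*.
- PET amount by tracer injection = 0.14 × 2 × *w* = 0.28 *w* mg; ratio = 0.7 *w*.

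| Assumed weight | PET total | Ratio to 0.4 mg | PET by 2 min | Ratio to 0.4 mg |
|---|---|---|---|---|
| 50 kg | 28.0 mg | 70 | 14.0 mg | 35 |
| 70 kg | 39.2 mg | 98 | 19.6 mg | 49 |
| 100 kg | 56.0 mg | 140 | 28.0 mg | 70 |
| 120 kg | 67.2 mg | 168 | 33.6 mg | 84 |

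The total ratio is exactly 100 at 100 × 0.4 / 0.56 = 71.4 kg. For regadenoson the ratio is 0.4 / 0.4 = 1 at every weight.

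**Route to the endpoint.** Take one modality and let *d* be the difference in measured stress flow (or CFR) that using one agent rather than the other would make. A subject with the same agent at both visits contributes no *d* to the change score; a subject who switches contributes +*d* or −*d*. If a proportion *p* switch, equally often in each direction and irrespective of arm, the mean shift is 0 in each arm and the variance of change rises by *p* × *d*². The documents give neither *p* nor *d*, so the size cannot be computed. They do allow *p* above 0, because the choice is discretionary and no text fixes the agent within a subject.

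**Sample size.** None of its inputs involves the stress regimen. With 68 evaluable subjects (34 per arm), SD 0.93, difference 0.69 and two-sided 0.05, a t-test has power 0.854, which agrees with the stated 85%.

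**The case against.** The strongest reply is that PET and MRI are separate procedures and may properly use different regimens. No text says that they must match. That stands: the two section V descriptions are not a logical contradiction on their own. What remains is the unexplained gap against a common regadenoson amount, and the conflict between the MRI bolus and the infusion wording in section VII.

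A reader might infer that unequal stress stops CFR and sMBF from standing in for each other. The documents do not support that as the harm. CFR is a ratio and sMBF a flow, so identical stress would not make them exchangeable. No text treats them as interchangeable; section I presents stress flow on MRI as another marker.

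A reader might also infer bias in the treatment comparison. That is not shown either. A PET/MRI difference applies to both arms and both visits, the trial is double-blind, and the PET and MRI images are read blinded to assignment. The 12-month visit repeats Baseline Visit 1, but that entry does not name the agent, so it does not settle whether a subject keeps the same one.

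The ratio is not a measure of stress. It sets a sustained infusion against a single bolus, and counting only to tracer injection halves it. Whether the two regimens dilate the vessels equally is a pharmacological question that the documents leave open. Likewise, the MRI adenosine figure equals the regadenoson figure beside it, but that does not establish a copying error or show which section is wrong. Section VII does provide for attended monitoring, treatment of severe side effects and stopping; these provisions limit the safety concern but do not reconcile the figures.

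**Conclusion.** The point holds as an inconsistency between three passages that needs reconciling. Delivery differs for both agents between PET and MRI, and the amount differs for adenosine only: 0.56 mg/kg against 0.4 mg. The ratio of 70 to 168 rests on assumed weights of 50 to 120 kg, but a large gap remains at any plausible adult weight.

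The consequence for the analysis is conditional. Extra measurement error in change within a modality requires both that the agents as written stress unequally and that some subjects change agent between visits. The documents establish neither, and they do not show that any subject received either adenosine regimen. The safety consequence is likewise conditional on one of the figures being wrong. No bias between arms and no change to the sample-size figures follows. No position is taken on which regimen is right.

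**What to change.** Before use, reconcile the PET and MRI descriptions in section V with the Regadenoson/Adenosine paragraph in section VII. The imaging and pharmacy leads should check agent, amount, route and timing for each modality, and the protocol should state them in one place. If the regimens are meant to differ between modalities, give the reason.

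State also whether a subject receives the same agent at baseline and month 12 within each modality. Recording the agent used at each scan would let any switches be counted.

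The cost is a protocol correction and one check by the two leads. The sample size and the planned treatment comparison need no change on this account.
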